Final success of any clinical trial in answering the question of interest depends in large part on its design. The term "quality by design" refers to steps taken at the trial-design stage to foresee and limit problems that might occur during the trial conduct. Adherence to the following 5 "guiding principles" greatly increases the chances of final success:

- 1. Have we enrolled the right participants according to the protocol with adequate consent (Right Patient)?
- 2. Did participants receive the assigned treatment and did they stay on the treatment (Right Treatment)?
- 3. Was there complete ascertainment of primary and secondary outcome data (Right Outcomes)?
- 4. Was there complete ascertainment of primary and secondary safety data (Right Outcomes)?
- 5. Were there any major Good Clinical Practice (GCP)-related issues?

This trial was designed to maximize the likelihood that the 5 principles noted above will be followed. In particular, participant enrollment and consent is facilitated by the carefully selected and operationalized CDRNs that are the cornerstone of the PCORnet initiative. Participant selection facilitated by EHRs should lead to efficient identification and enrollment of patients who satisfy study eligibility and enrichment criteria. These criteria have been chosen in a manner that corresponds to what is routinely available in EHRs, reducing the risk of any ambiguity and enrollment of patients who do not meet the protocol-specified criteria.

Although it is not possible to guarantee that all study participants will remain on the trial until its end and fully adhere to the study drug, the existence of the ADAPTABLE patient portal and potential follow-

up from the DCRI Call Center are expected to keep participants engaged and help them maintain their assigned treatment by regularly asking them about the treatment they take. At the same time, because this trial is intended to describe what happens in a "real-world" population (ITT principle), variability in treatment adherence may actually contribute to better generalizability of study results.

Similarly to the eligibility criteria, primary efficacy and safety endpoints have been defined in a way that is well synchronized with the endpoint collection tools that will be employed. The focus on "hard" endpoints (that is, endpoints that can be unambiguously determined), cause-specific hospitalizations for MI, stroke, and bleeding, greatly reduces the potential of recall bias by study participants during self-report. At the same time, it facilitates improved ascertainment through the corresponding EHRs. Accordingly, the CRFs are short and questions are phrased in a manner that does not overwhelm study participants. Access to EHRs and consent to search death records should also reduce the amount of missing primary endpoint data. Minimal levels of intervention and a focus on observing rather than influencing the study participants greatly increases the likelihood that GCPs will be followed.

III.G.2. Study Network

The Study Network of recruiting sites is composed of CDRNs and HealthCore/Anthem Research Network (HCARN), an HPRN, within PCORnet. Each of these CDRNs and the HPRN have developed a specific plan to engage clinicians, identify and recruit eligible participants, and facilitate participant follow-up in the trial. The Coordinating Center will perform specific centralized functions; this will be advantageous to meet study budget limitations.

[figure not shown]

Figure 1. ADAPTABLE Leadership Structure

III.G.3. Executive Committee

The ADAPTABLE Executive Committee will provide oversight and guidance for overall trial activities. It will also serve as a communication nexus to promote sharing of information and cross-pollination of ideas among the Executive Committee, Steering Committee, study co-principal investigators (PIs), Coordinating Center PIs and staff, PCORI representatives, and the co-chairs of the Patient Representatives/Adaptors group, all of whom will have representation on the Committee. The decision-making structure and process for the Executive Committee will be described in a study leadership charter.

III.G.4. Steering Committee

The trial's Steering Committee will be responsible for the protocol and the scientific conduct of the study. The Committee will include patient and clinical representatives from each participating CDRN, HPRN, and PPRN, along with selected network members with expertise in clinical research in antiplatelet therapies, cardiovascular disease, and analytical methods. Additionally, representatives from the American College of Cardiology, the American Heart Association, and PCORI will be on the Steering Committee. The Steering Committee will make decisions about any changes to the protocol and will review all proposed substudies. The decision-making structure and process for the Steering Committee will be described in a study leadership charter.

III.G.5. Data and Safety Monitoring Board (DSMB)

The DSMB will consist of independent members who are not participating investigators in this trial. The committee will include a chair who is a cardiovascular specialist, a statistician, 2 patient representatives, and 3 cardiovascular specialists. The DSMB will review data regularly and recommend necessary changes to the conduct of the trial. For example, if significantly large and important treatment differences are observed during any of the interim analyses, the DSMB may recommend that randomization of patients be stopped, or that the design and conduct of the trial be appropriately modified.

We anticipate that the DSMB will meet at approximately 6-month intervals to review the accumulating data. Before each DSMB meeting, the Data Coordinating Center will conduct the desired statistical analyses and prepare a summary report for review by the DSMB. The extracted data files and analysis programs for each DSMB report will be maintained at the Data Coordinating Center for the life of the study. Each report will describe the progress in enrollment and the rates of compliance with therapy.

The DSMB may recommend stopping the trial for any safety-related concern at any time. Particular attention will be paid to all-cause mortality. For effectiveness, the trial will compare doses of aspirin that have been proven effective in previous trials, and thus it is unlikely that any dramatic differences will appear early. However, the DSMB will monitor these differences about every 6 months over the 3.5 years of the trial. Thus, we anticipate 6 interim analyses and 1 final analysis. Because there are multiple tests, each test must be made at an adjusted alpha level using group sequential-testing methods. To minimize the chance of stopping early due to a spurious result, the endpoints will be tested at the planned analyses using a specific method known as the Haybittle-Peto rule. 101 This rule tests the

endpoints at the 0.001 level (z = 3.29, two-sided) at each interim review and then makes the final test at the 0.0499 level (z = 1.9605). Thus, there is only minimal penalty for interim analyses.

The decision-making structure and process for the DSMB will be described in a separate DSMB charter.

III.G.6. Data Auditing Conventions

Data will be collected via the study patient portal (Sections III.A.3.c and III.A.3.h).

IV. Human Subjects

IV.A. Protection of Human Subjects

IV.A.1. Sources of Data

Data obtained from the study participant web portal, from the CDM, from Centers for Medicare Services, and from HealthCore/Anthem Research Network, an HPRN, will be transferred to the DCRI along with unique participant identifiers. Details for the process and authorization for Medicare and health plan data linkages are contained in a separate Linkage Plan document. Data contained within the CDM will be obtained from each of the recruiting sites and the HPRN and will be transferred to the DCRI. The control of access to databases at DCRI will be managed centrally by the DCRI through user passwords linked to appropriate access privileges. This protects data from unauthorized view and modifications as well as inadvertent loss or damage. Within the secondary SAS databases, UNIX group access control will be used for maintaining similar security. The Sun workstation login will be secured by extensive user password facilities under UNIX.

IV.A.2. Potential Risks

Aspirin is approved by the US FDA for the secondary prevention of ischemic events associated with ASCVD. In patients with established atherosclerosis, the risk of aspirin is quite low compared with the benefit. A very small number of patients have a serious anaphylactic reaction or bronchoconstriction with nasal polyps when they use aspirin. The risk of intracranial hemorrhage is less than 0.04% per year. A modest number of patients develop serious GI bleeding as a result of loss of the protective effect of prostaglandins on the gastric mucosa. A larger number of patients have GI intolerance, but this is often transient and can be overcome. The absolute risk varies as a function of the trial entry criteria, but none of these major risks exceeds 5 events per 100 patients treated per year. Except for patients with preexisting asthma, no studies have described risk factors for these complications of aspirin use. However, because participants will be selected based on the absence of such known major intolerances to a dose of 325 mg of aspirin, the expected risk of these major events in this trial will be low.

IV.A.2.a. Recruitment and Informed Consent

Each CDRN and the HPRN will develop a specific recruitment process that will work best within their organization, utilizing the tools they have available and their local infrastructure. Prior to cohort identification, site investigators and clinicians will be asked to endorse the protocol, and depending upon their preference, they will either determine each patient's eligibility or will give permission for the

CDRN, through its integrated health system members, to identify and contact potentially eligible patients. Patients who meet trial inclusion criteria will be identified using electronic search algorithms adapted to each network from their aggregated EHR systems. Broad agreement from both cardiovascular specialists and primary care physicians will be sought to enroll eligible participants. Participants will be enrolled after providing electronic informed consent via the study participant portal either directly for those participant s with internet access or via a process facilitated by site research staff during clinic encounters for patients without internet access.

IV.A.2.b. Protection Against Risk

See Sect. IV.A.1. (Sources of Data) above and Section IV.E. (Data and Safety Monitoring Plan) below.

IV.A.2.c. Potential Benefits of the Proposed Research to the Research Participants

As discussed in **Section I.A.**, atherosclerosis leading to thrombotic events, and in particular ASCVD, represents the leading cause of death, morbidity, and disability and affects more than 150 million people worldwide. Despite remarkable progress in preventive and interventional approaches to atherosclerosis, ASCVD is expected to be an even more prominent cause of death and disability for the next 30 years. In technologically developed countries, the major factor that contributes to this expansion is the aging of the population, such that, despite declining age-specific disease rates, the total disease burden increases because ASCVD eventually strikes a larger population of older adults. In developing countries, a major epidemic of atherosclerosis is occurring, concentrated at younger ages and presumably due to the spread of tobacco use, Westernization of diet, and a sedentary lifestyle.

The development of new biological and technological approaches to treating ASCVD is exciting, but maximizing the use of an inexpensive yet effective therapy is far more promising in reducing death and disability on a global scale. Numerous clinical trials have shown the clinical benefit of aspirin vs placebo in reducing vascular events, but the best dose of aspirin for the general population with ischemic heart disease has not been determined. Considering the global burden of ASCVD and that the affected population is growing rapidly, identifying the optimal dose of aspirin would save lives and prevent ischemic and bleeding events globally.

IV.A.2.d. Importance of the Knowledge to Be Gained

The primary aim of this study is to determine the optimal dose of aspirin, the universally available effective therapy for ASCVD. Despite dozens of clinical trials involving over 100,000 patients, the most effective aspirin dose has not been identified. Nonrandomized studies have suggested that lower doses of aspirin may be associated with not only lower rates of bleeding but also reduced ischemic outcomes. Despite guideline recommendations for lower-dose aspirin, over half of post-ACS patients in the US are discharged on a dose of 325 mg. Considering the worldwide epidemic of ASCVD and the potential benefits of aspirin, identifying the optimal dose of aspirin would have substantial global health and economic effects similar to few other medical therapies.

Although the primary aim of this study is to determine the optimal dose of aspirin, this study also represents a new and efficient interactive model for designing and implementing clinical trials that aim

to refine therapies already in use in contemporary clinical practice. Because we live in an era in which the number of effective (or potentially effective) therapies far exceeds our ability to evaluate them in prospective clinical trials using current methods, there is an urgent need to develop an approach to outcome-based trials that can greatly reduce the cost per participant. By following participants directly on the internet and thereby avoiding the costs of clinic visits, lengthy case record forms and extensive site management, we believe that a new, more efficient, and less expensive model for trials can be developed that could be extended to more experimental comparisons. However, working through the issues of informed consent, data validation, events ascertainment, and compliance assessment will require acceptance of novel approaches to statistical sampling and an intense focus on communication with both patients and their physicians. In this era of increasing concern about both patient privacy and research integrity, such an approach to trial efficiency would be exceedingly difficult to pilot with untested therapies. Because this trial will test only doses of aspirin that are considered relatively safe and are widely used in current clinical practice, it provides a critically and globally important clinical issue with which to develop such new clinical trials methods.

This trial also provides an opportunity to explore the use of integrated health systems, EHRs, and patient-reported outcomes as tools for performing clinical trials. A trial conducted almost exclusively over the internet offers many potential benefits. First, participants would have access to a custom-built, patient-centered participant portal that offers current information about symptom awareness, risk factor modification, and disease management and prevention. The participant portal would also serve as the primary mechanism for follow-up, with routine data entry by the participant themselves. Not only would this method examine the practicability of participant self-reporting, but it would potentially enable substantial savings in cost and resources (e.g., costs associated with physician reporting). For physicians, use of the internet in clinical trials could further broaden awareness and participation and, at the same time, facilitate the conduct of the study. For example, trial enrollment and follow-up could be immediate with use of the internet, at any time, eliminating a need for traditional methods (e.g., face-to-face visits). Finally, the platform created by this trial will unite a far-reaching community of patients and their physicians with a common goal of refining an existing therapy to maximize its benefit relative to risk. It is likely that such knowledge will produce far greater global benefit than the introduction of many other "high-tech" approaches.

IV.B. Diminution of Barriers

This study will seek to enroll a diverse population representative of the broad population of patients with ASCVD. The CDRN medical practices are from communities representing both sexes, a wide range of ages, and varied racial and ethnic backgrounds. We will make every attempt to explain the project in easy (non-clinical) terms to all participants to make sure they understand the importance of the research and the need to have good representation of key subgroups and they appreciate the potential benefit they could derive from participating in it. A particular advantage for this trial is the relative lack of barriers to participation. Because clinic visits are not needed for follow-up, additional transportation is not required, and there is minimal additional time commitment for participants. With regard to the specific enrollment of women, this is discussed in detail in **Section III.A.2.a-b**. Strategies to enhance the

enrollment of ethnic minorities are also described in detail in **Section III.A.2.a-b.** We will strive to enroll a proportion of minority patients similar to that in the overall ASCVD population. Content on the ADAPTABLE patient portal will be available in English and Spanish.

IV.C. Inclusion of Children

Because participation in this trial is restricted to patients aged 18 years and over, inclusion of children in this trial is prohibited. Since the incidence of coronary artery disease among young (i.e., less than 18 years) individuals is very low, children do not represent a study population relevant to this trial.

IV.D. Data and Safety Monitoring Plan

This has been described in detail in **Section III.A.7** (Data and Safety Monitoring Board).

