Notwithstanding the relative lack of randomized evidence regarding the optimal dose of aspirin when it is used together with a P2Y₁₂ inhibitor during DAPT treatment, recently published US guidelines for the duration of DAPT treatment give a Class IB-NR recommendation for the use of low-dose aspirin (< 100 mg/day) when aspirin is used together with any P2Y₁₂ inhibitor. ⁴⁴ The data supplement within the guidelines document underlying this specific recommendation cites numerous nonrandomized, post-hoc analyses that have investigated different aspirin doses both with and without concomitant use of P2Y₁₂ inhibitors, except for the aforementioned CURRENT-OASIS 7 trial²⁴ that evaluated patients for only 30 days after the index ACS event. However, the guidelines committee specifically endorsed the goals and objectives of the ADAPTABLE trial to determine the optimal dose of aspirin with concomitant DAPT treatment.

In summary, the appropriate dose of aspirin in conjunction with a $P2Y_{12}$ inhibitor is unknown despite the recent guidelines recommendation. The ADAPTABLE trial investigators recognize the equipoise and uncertainty that exist regarding this important clinical question and will investigate this issue by conducting a subgroup analysis according to the concomitant use of a $P2Y_{12}$ inhibitor. Patients who are treated with either clopidogrel or prasugrel will be eligible to be included in the study, but patients treated with ticagrelor will be excluded, given the FDA "black box" warning for the use of high-dose aspirin with ticagrelor. $\frac{43}{2}$

II.C.4. Systematic Reviews and Mechanistic Insights into Aspirin Dosing

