Patients who are identified as candidates for the trial will be directed to the ADAPTABLE patient portal for the eConsent as well as an abbreviated eligibility confirmation prior to randomization. The ADAPTABLE patient portal will include the electronic patient consent (eConsent) that satisfies the local IRB and state law requirements of the participating CDRNs and HRPN. CDRN personnel will be available, if needed, to give a more local perspective on protocol-related consultations. For patients without internet access, patient consent via the ADAPTABLE patient portal will be obtained during a process facilitated by site research staff during clinic encounters, and follow-up will be done via telephone contact with the DCRI Call Center.

Patients will be randomized via the patient portal in a 1:1 ratio to receive 81 mg vs 325 mg of aspirin. Patients will be asked to obtain their randomized aspirin dose at their local pharmacies. The randomization scheme will be established before the inception of enrollment. In a trial of this size, stratified randomization has no significant advantages.

After randomization, during the early first web portal contact or telephone contact (for patients without internet access) from 1 to 3 weeks after randomization, patients will be asked to answer questions related to current aspirin use and dose and other specific concomitant medications. They will also be asked to provide contact information such as their name, email and home address, phone numbers, and

contact information for a family member or friend not living with them. These data will be used to contact patients who miss multiple visits and to identify events such as hospitalizations that occur out of network. The enrolling sites will be responsible for ensuring that randomized patients complete their early first contact visit (1-3 weeks after randomization).

Neither patients nor healthcare providers will be blinded to their treatment assignment, as blinding would add substantial complexity and cost without commensurate incremental benefit. The "hard" outcomes, large sample size, and equipoise in the clinical community should enable valid results to be obtained, and we have no reason to believe that investigator or clinician bias will play a role in ascertainment or classification of events.

III.C.3. Concomitant Therapy

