Key concomitant medications will be self-reported by the participant and over time will also be harvested from the PCORnet DataMart in CDM version 3.0 as it is deployed. Pre-randomization aspirin dose for aspirin users will be recorded. Participants will report key concomitant medications annually, either on the participant portal or during phone follow-up calls from the DCRI Call Center.

Details on the use of aspirin and important concomitant medications (P2Y₁₂ inhibitors) and other over-the-counter medications of interest (nonsteroidal antiinflammatory drugs [NSAIDS] and proton-pump inhibitors [PPIs]) will be collected from participants at baseline and annually during study follow-up. Details on other common secondary prevention medications prescribed (beta-blockers, angiotensin-converting enzyme inhibitors/angiotensin receptor blockers, and statins) will be collected from the CDM. The large trial population and randomization will minimize potential biases and confounding that could result from differential use of concomitant medications by randomized treatment assignment. A sensitivity analysis that accounts for concomitant medications as time-dependent covariates will be done to account for post-randomization treatments.

III.C.4. Schedule of Assessments

ADAPTABLE SCHEDULE OF ASSESSMENTS*

	Baseline	1-3 Week Follow-up Post-Randomization	Every 3 or 6 Month Follow-up	Annual Collection	End of Study
			*Assessments collected every three or six months based on randomization	Replaces 3M /6M follow up	
Video describing trial expectations	Х				
Check Key Eligibility Review	х				
Sign e-Consent	х				
Randomization and dose assignment	х				
Collect pre-randomization aspirin dose		x			
Collect demographic/contact information	X	Х			
Collect key concomitant (Rx and OTC) medications		х		х	х
Collect current aspirin dose/reason for DC		х	x	х	х
Collect hospitalizations		x	x	X	x
Collect Patient Reported Outcomes (PRO)	x		Q6 months		x
Insurance info/Confirmation at Contact info		x			

^{*}All Baseline and 1-3 Week Follow-up Post Randomization visit data will be collected at the Baseline visit for all non-internet patients with the exception of the current aspirin dose. The current aspirin dose will be collected 1-3 weeks following randomization.

III.C.5. Data Collection and Follow-up

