2. **Pattern-mixture approach.** Following Little et al., ^{98,99} we will assume that for participants who drop out, the hazard of an outcome deviates from that of participants who do not drop out by an offset, denoted by *d1* for the higher dose and by *d0* for the lower dose. We will then explore the effect of this deviation on the findings for various choices of the offsets in the 2 study groups. If the treatment effect is qualitatively maintained for the range of offsets that are considered to be clinically plausible, then the findings will be considered to be robust.

In other analyses, missing data will be handled using multiple imputations. Ten imputed data sets will be generated with imputation methods based on the regression or Monte Carlo framework. Final results will be based on averages from the 10 imputed data sets with appropriate estimator employed of the variance. 99

III.F.9. Subgroup Analyses (Heterogeneity of Treatment Effect)

Subgroup analyses for the primary effectiveness and safety endpoints will be performed on the ITT population to explore whether the treatment effect is consistent across subgroups. Subgroup analyses to evaluate variation in treatment effect will be performed on the basis of tests for interaction using the Cox proportional hazards model with terms for treatment group, the subgroup variable, and treatment by subgroup variable interaction. Additionally, treatment effects within each categorical subgroup will be examined separately using Cox proportional hazards models. Event rates by treatment and HRs with 95% CIs will be reported for each subgroup. Forest plots will be generated displaying the estimated HRs, and 95% CIs for each subgroup will be presented. For subgroups defined using continuous variables, the analysis based on the continuous form will be considered primary, but for display purposes these variables can also be categorized.

The following subgroups determined at baseline will be examined:

- Age 65 years or older
- Race and ethnicity categories (white, Black, and Asian race; Hispanic ethnicity)
- Diabetes mellitus
- Chronic kidney disease (serum creatinine 1.5 mg/dL or greater)
- Current P2Y₁₂ inhibitor use
- Female sex

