7.11 Subgroup Analyses (Heterogeneity of Treatment Effect)

Subgroup analyses for the primary effectiveness and safety endpoints will be performed on the ITT population in order to explore whether the treatment effect is consistent across subgroups. Subgroup analyses to evaluate variation in treatment effect will be performed on the basis of tests for interaction using the Cox proportional-hazards model with terms for treatment group, the subgroup variable and treatment by subgroup variable interaction. Additionally, treatment effects within each categorical subgroup will be examined separately using Cox proportional-hazards models. Event rates by treatment and HRs with 95% confidence intervals will be reported for each subgroup. Forest plots will be generated displaying the estimated hazard ratios and 95% confidence intervals for each subgroup. For continuous variables, the linearity assumption will be checked for violations using natural cubic splines. In the event that major violations are found, natural cubic splines will be used in the final model. This analysis will be considered primary, but for display purposes, these variables will also be categorized.

The following variables determined at baseline will be examined:

- Age (continuous)
- Race categories (White, Black, and Asian; Hispanic ethnicity)
- Diabetes mellitus
- Chronic kidney disease (serum creatinine > 1.5 mg/dL)
- P2Y12 inhibitor use
- Female sex

We expect homogeneity of treatment effect across subgroups following the results observed in the full sample. Thus, testing for differences between treatment arms within subgroups will be considered exploratory and no claims of heterogeneity will be made based on tests within subgroups.

As a sensitivity analysis, the interaction between randomized treatment arm and internet vs noninternet enrollment will be assessed for the primary efficacy and safety outcomes.

8 Tables and Figures

See appendices for Table Shells.

9 References

Little R.J., D. R. (2012). The Prevention and Treatment of Missing Data in Clinical Trials. *N Engl J Med*, 367:1355-1360.

RJ Little et al. The treatment of missing data in a large cardiovascular clinical outcomes study. Clinical Trials 2016

Liublinska V, and Rubin DB (2014). Sensitivity Analysis for a Partially Missing Binary Outcome in a Two-Arm Randomized Clinical Trial. *Stat Med*, 33(24):4170-4185.

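### P2Y12 inhibitor use is analysed as a baseline subgroup, but the schedule collects it 1-3 weeks after open-label randomization for internet participants, and the SAP names no source or time window

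*Protocol*

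**What the plan says.** **Status of the variable.** P2Y12 inhibitor use is a named Aim 2 comparison, and SAP 2.1.2 specifies treatment at baseline. Protocol III.F.9 introduces its list, which includes current P2Y12 use, with "The following subgroups determined at baseline will be examined". SAP 7.11 does the same with "The following variables determined at baseline will be examined".

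**Timing.** The passages disagree:

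- Protocol III.C.3, text: details of P2Y12 use "will be collected from participants at baseline and annually during study follow-up".
- Protocol III.C.4, schedule: the row "Collect key concomitant (Rx and OTC) medications" has nothing under Baseline. It is marked at the 1-3 week post-randomization contact, annually and at end of study.
- Protocol III.C.2: at the web or telephone contact 1 to 3 weeks after randomization, "patients will be asked to answer questions related to current aspirin use and dose and other specific concomitant medications".
- Schedule footnote: "All Baseline and 1-3 Week Follow-up Post Randomization visit data will be collected at the Baseline visit for all non-internet patients", with current aspirin dose as the only exception.

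**Blinding.** Protocol III.C.2: "Neither patients nor healthcare providers will be blinded to their treatment assignment".

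**Source.** Protocol III.C.3 assigns P2Y12 use to participant report and contrasts it with beta-blockers, ACE inhibitors/ARBs and statins, which come from the Common Data Model (CDM). It adds that key medications will also be taken from the CDM as that is rolled out. SAP 7.11 names no source or window, and the CDM medical-history list in SAP 7.1 does not include P2Y12 use.

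**The concern.** A subgroup comparison keeps the protection of randomization only if membership is fixed before assignment. If membership rests on what a participant reports one to three weeks later, when participant and clinician both know the dose, the two arms of the user group need not be comparable. The same holds for the non-user group, because anyone who leaves one group joins the other.

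The subgroup matters. Protocol II.C.3 says that current US guidelines "give a Class IB-NR recommendation for the use of low-dose aspirin" when a P2Y12 inhibitor is also taken. It offers this subgroup analysis as the trial's contribution to a question it regards as open.

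Protocol III.C.3 recognises that concomitant medication may differ by assigned arm, and answers that trial size and randomization will limit the effect. Randomization does not balance a variable that is measured after it.

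**Working it through.** No figure in the documents depends on this point, so none can be reproduced. The check is a reading of the passages, followed by illustrations with assumed inputs.

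**1. Is the empty Baseline cell a table-reading fault?** Probably not. III.C.2 gives the same timing in words, and the footnote would be unnecessary if the item were already collected at Baseline for everyone.

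**2. Does the question look back to before randomization?** Nothing says so. The schedule has a separate item for pre-randomization aspirin dose and no counterpart for P2Y12 use. The Protocol subgroup is worded as current use.

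**3. Are non-internet patients clear of the problem?** Not fully. The footnote puts their answers at Baseline, while III.C.2 describes the 1-3 week telephone contact for them as well. Randomization is itself a Baseline item, and no order relative to the medication question is given.

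**4. Does a planned analysis repair it?** No. The 10-day landmark (Protocol III.F.7, SAP 7.8) removes early events but does not redefine the subgroup. The time-dependent medication analysis (Protocol III.C.3) concerns later treatment, not membership.

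**5. Effect on the hazard ratio among users.** Assumptions: true HR 1; s325 and s81 are the shares of users who stop before reporting; the users who stop only under 325 mg have r times the risk of the rest.

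HR (325 vs 81) = (1 − s81) / [(1 − s325) + (s325 − s81) × r]

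With s81 = 0.02:

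| s325 | r = 0.5 | r = 1 | r = 1.5 | r = 2 |
|---|---|---|---|---|
| 0.05 | 0.98/0.965 = 1.016 | 1.00 | 0.98/0.995 = 0.985 | 0.98/1.01 = 0.970 |
| 0.15 | 0.98/0.915 = 1.071 | 1.00 | 0.98/1.045 = 0.938 | 0.98/1.11 = 0.883 |

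Equal stopping in both arms also gives 1.00.

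**6. Effect on the interaction test,** which is what the plan uses to judge heterogeneity. Assumptions: users are a share p = 0.2-0.3 of patients, with 1.3 times the event rate of non-users; a share f of users stop, in the 325 mg arm only; stoppers have q times the risk of other users; 1322 events in total (Protocol III.F.5).

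Worked case, p = 0.3, f = 0.05, q = 2:

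- HR among users = 1/(1 − f + f × q) = 1/1.05 = 0.952.
- Event rate of the remaining users, relative to non-users = 1.3/1.05 = 1.238.
- HR among reported non-users = (0.7 + 0.3 × 0.05 × 2 × 1.238)/(0.7 + 0.3 × 0.05) = 0.7371/0.715 = 1.031.
- Ratio of the two = 0.952/1.031 = 0.924.
- With about 450 events in users and 872 in non-users, SE = √(4/450 + 4/872) = 0.116 and z = ln(0.924)/0.116 = −0.68. A two-sided 5% test then rejects about 10.5% of the time.

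Across p = 0.2-0.3:

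| f | q = 0.5: ratio (rejection) | q = 1: ratio | q = 2: ratio (rejection) |
|---|---|---|---|
| 2% | 1.01 (5%) | 1.00 | 0.97 (6%) |
| 5% | 1.03 (6%) | 0.99-1.00 | 0.92-0.94 (8-11%) |
| 10% | 1.06-1.07 (7-9%) | 0.99 | 0.86-0.88 (16-25%) |

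**7. Events before the report.** Assume a constant rate of 4.2-5.5% a year (the lowest overall rate in Protocol Table 6; the original higher-risk-arm rate in SAP 7.6). Expected primary events among 15,000 = 15,000 × rate × days/365.25, which is 12-16 by day 7 and 36-47 by day 21. Some are deaths, and an internet participant who dies before the contact cannot report. SAP 7.9 covers missing outcome dates, event follow-up and longitudinal outcomes, but not a missing subgroup variable.

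**The case against.** The strongest reply has five parts.

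- **The mechanism is not documented.** A reader might infer from the guideline that clinicians would stop the P2Y12 inhibitor in patients assigned 325 mg. The documents do not support that. The recommendation concerns aspirin dose; a clinician acting on it would alter aspirin, which is crossover handled by intention to treat (Protocol III.C.5.a), and P2Y12 status would not change. This stands. What remains is the general exposure: assignment is known, and III.C.5.a asks providers to leave the aspirin dose alone without any such request for P2Y12 therapy.
- **The subgroup's source is unstated.** It might be the CDM, or the form might ask about use at enrolment; its wording is not in the documents. This also stands, and it is why the point is a possibility and not a demonstrated bias. If either was intended, a sentence in the SAP would settle it.
- **Participants who miss the contact are not necessarily without a value.** The annual collection and the CDM may supply one, sites must ensure the contact is completed, and Protocol III.F.8 provides multiple imputation for other analyses. The supportable statement is that no classification rule is given. An annual report is also later still.
- **A range showing only hazard ratios below 1 would mislead.** Those who stop could be at lower risk, which reverses the direction.
- **Within-subgroup tests are exploratory, and interaction power is conceded to be limited.** True, but limited power does not protect the interaction test from a membership bias.

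**Conclusion.** The Protocol contradicts itself on when P2Y12 use is collected, and the SAP does not resolve it. Followed as scheduled, the plan would define a named Aim 2 subgroup after open-label assignment for internet participants, so this is more than a missing detail. Whether it would bias the result cannot be determined. The documents give no rate of early P2Y12 change, no evidence that it would differ by arm, and no link to risk.

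Under the assumed stopping rates, a null hazard ratio among users would be displaced to somewhere between about 1.07 and 0.88. It would not move if stopping is unrelated to risk or equal in the arms. The larger displacements need frequent, arm-specific and risk-related changes within three weeks, so a small effect or none is quite possible.

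Two stronger readings should be resisted: that the subgroup result will be biased in favour of 325 mg, and that the main result is compromised. The direction is unknown, and the primary intention-to-treat comparison does not use this variable.

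**What to change.** 1. Reconcile Protocol III.C.2, the III.C.3 text, the schedule and its footnote. Either collect P2Y12 use before randomization for everyone, or ask explicitly about use on the day of randomization.
2. In SAP 7.11, define the subgroup as P2Y12 use on or before the randomization date. State the source, the time window, and how patients without a 1-3 week contact are classified.
3. Add a sensitivity analysis of the treatment-by-P2Y12 interaction, using CDM or claims prescription records dated on or before randomization.
4. If only the post-randomization report exists, label the subgroup as such wherever it is reported.

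The cost is some wording and one more derivation. CDM records are better suited to the sensitivity analysis than to serve as the sole primary definition. Medication data arrive as the CDM is deployed, and Protocol Table 4 lists no medication domain, although the text below it says that all essential data other than aspirin dose and certain over-the-counter drugs are in CDM 3.0. Out-of-network prescriptions may be missed. For records dated before randomization that loss cannot depend on the assigned dose, but it could dilute the interaction in that analysis.
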